**13.2.1. Excessive early mortality**

Early stopping rules for excessive mortality will be applied in the safety phase of the study. Early mortality is defined for this study as death due to any cause within 30 and 60 days of the initiation of study treatment. In the VALOR trial, all-cause mortality rates of 7.9% and 19.7% were reported, respectively, for patients with relapsed/refractory AML who received cytarabine and placebo as induction therapy. [14] The 30-day mortality rate of 7.9% from the VALOR trial is similar to the 28-day mortality rate of 10.3% that was reported from a retrospective analysis of more than 3000 patients with newly diagnosed AML, the majority of whom were treated with cytarabine-based regimens as induction therapy.[11]

Based on the above considerations, enrollment in a cohort will be halted if the observed 30- and 60-day early mortality rate exceeds 10% and 20%, respectively, as follows: if 1 or more of the first 6 patients enrolled within a cohort die prior to Day 30 then enrollment of additional patients within that cohort will be halted pending review by the Protocol Safety Committee. Additionally, enrollment will be halted within a cohort if 2 or more of the patients die prior to Day 60. Otherwise, 6 additional patients will be enrolled within the cohort provided none of the other stopping criteria have been met.

For the second group of 6 patients within a cohort, if 2 or more of the patients enrolled within a cohort die prior to Day 30, then enrollment of additional patients will be halted pending review by the Protocol Safety Committee. Similarly, if 3 or more of the patients enrolled within a cohort die

prior to Day 60, then enrollment of additional patients will be halted for that cohort. If these and the other early stopping criteria are not met, then the 12 additional patients will be enrolled within the cohort.

### **13.2.2. Excessive expected crenolanib-related toxicity**

Early stopping rules for excessive expected crenolanib-related toxicity will be applied in the safety phase of the study. In clinical studies of crenolanib as single-agent therapy, the following treatment-related, non-hematologic, adverse events were the most frequently reported, irrespective of severity:

- hepatic dysfunction
- nausea, vomiting, and diarrhea
- ascites, edema, and effusions

The majority of these events were CTCAE severity grade 1-3, with grade 4 representing less than 5% of total cases reported. It's anticipated that these or similar adverse events also occur with relatively higher frequency for AML induction regimens that include cytarabine, idarubicin, or daunorubicin. Nonetheless, for purposes of monitoring enrollment in this study, the adverse events listed above represent the expected non-hematologic crenolanib-related toxicities. If the observed rate of expected, non-hematologic, crenolanib-related toxicity with CTCAE severity grade 4 exceeds 20% during the first 60 days of treatment, then enrollment will be halted as follows:

If 2 or more of the first 6 patients enrolled within a cohort experience a CTCAE grade 4, non-hematologic, expected crenolanib-related adverse event prior to Day 60 then enrollment of additional patients within that cohort will be halted pending review by the Protocol Safety Committee. Otherwise, 6 additional patients will be enrolled within the cohort provided none of the other stopping criteria have been met. Upon enrollment of the 6 additional patients within a cohort, if 3 or more of the patients enrolled within a cohort experience such an event prior to Day 60, then enrollment of additional patients will be halted pending review by the Protocol Safety Committee. If these and the other early stopping criteria are not met, then 12 additional patients will be enrolled to the cohort.

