#### 8.2.1. Induction

Patients with newly diagnosed AML with FLT3 activating mutations will be treated with crenolanib following induction with either daunorubicin/cytarabine or idarubicin/cytarabine. During the initial safety phase the anthracycline options will be separated into Cohort A and B. Induction treatment schedules combining standard 7+3 chemotherapy with crenolanib are listed in Tables 2 (Cohort A) and 3 (Cohort B). During the expansion phase, the choice of anthracycline will not be separated into different cohorts.

Crenolanib will start approximately 24-48 hours after completion of cytarabine (+7 day window). Adequate liver function including normal total bilirubin ALT and AST  $\leq 2.0 \times$  ULN are required within 24 hours prior to crenolanib commencement. Crenolanib can be delayed until this criterion is met. (If crenolanib will be delayed longer day 16, a discussion with PI and sponsor should be conducted to determine the best options for the patient)

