### **8.3. Treatment with Crenolanib (AR-868,596)**

The investigator or his/her designee is responsible for explaining the correct use of the investigational agent(s) to the subject or other site personnel such as inpatient staff, verifying that instructions are followed properly, maintaining accurate records of study drug dispensing and collection, and returning all unused and unopened medication to AROG or its designee at the end of the study. Study medication that has been dispensed but remains unused at the end of each cycle is recorded by the site personnel and either safely discarded if opened or returned to AROG if unopened with intact packaging.

Subjects will be instructed to contact the investigator as soon as possible if they have a complaint or problem with the study drug so that the situation can be handled.

**Missed Doses/Counting Cycle Days:** If a subject vomits after drug ingestion, no replacement dose is to be taken; the subject can continue to take the remaining doses as planned. If drug is held or a dose is missed by more than 3 hours after the scheduled time, the missed/held dose should not be made up. Dosing will resume with the next scheduled dose. The subject/nursing or research staff should enter in the diary the doses as missed and reason for missed dose. If drug is held or missed for a day or more, treatment should continue as if uninterrupted. As pill count for compliance assessment will be performed at each patient follow up; leftover drug should be returned to the study site by the subject upon follow up.

During induction and consolidation, one cycle is defined by start of chemotherapy and will continue until the start of next chemotherapy (i.e. induction 1 = cycle 1 and may exceed 28 days)

regardless whether drug is held. During maintenance, cycles will be 28 days in maximum duration (28 days = 1 cycle = 1 month).

“Days” of a cycle are to be counted sequentially from start of chemotherapy (not study drug) until start of next chemotherapy cycle. During maintenance, the start of a cycle is denoted by ingestion of the first dose of crenolanib after evaluation of efficacy at the end of induction or consolidation. The scheduled procedures/visits should comply with the study calendar regardless of amount of study drug administered.

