#### 13.1.2. Determination of sample size

A total of approximately 120 patients will be enrolled. The study consists of a safety phase and an expansion phase. The safety phase has two arms in which patients will receive cytarabine in combination with daunorubicin (Cohort A) or with idarubicin (Cohort B) during standard 7+3 therapy with Crenolanib. The safety of each arm will be evaluated separately and once the safety is established, an expansion phase will be opened in which patients can receive either chemotherapy regimens.

During the initial safety phase, the two cohorts, each consisting of approximately 24 patients, will be analyzed separately and initially enroll 12 patients to receive crenolanib with 1-2 courses of standard induction chemotherapy. If the early safety stopping criteria are not met for a cohort, then 12 additional patients may be enrolled in that cohort in order to further characterize the safety and tolerability of the combination.

Once the safety of the combinations is determined, a single arm expansion phase will be initiated to further confirm the safety and assess the clinical benefit of the combination of standard induction chemotherapy with crenolanib.

Historically, patients with newly diagnosed FLT3+ve AML achieve a 66% - 69% response rate with induction chemotherapy only. (Mandelli et al. J Clin Oncol. 2009;27(32):5397-403) In recent years, Midostaurin (a FLT3 TKI) has shown an improvement of response rate to 74-76% with the combination of Midostaurin to standard induction chemotherapy. (Schlenk et al. Blood 2016; 128(22): 449) This study will enroll approximately 120 patients with the following confidence intervals based on projected response rate. A response rate of 90% will have a 95% CI of  $\pm 5\%$ . That is to say that if we treat 120 patients and observe a 90% response rate, we are 95% sure that the true response rate is between 85% to 95%.

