### **13.2.3. Excessive unexpected crenolanib-related toxicity**

Early stopping rules for excessive unexpected crenolanib-related toxicity will be applied in the safety phase of the study. An unexpected crenolanib-related toxicity is defined as any non-hematologic, adverse event considered related to crenolanib (exclusive of those listed in Section 13.2.2). If the observed rate of unexpected, non-hematologic, crenolanib-related toxicity with CTCAE severity grade 4 exceeds 15% during the first 60 days of treatment then enrollment within a cohort will be halted as follows:

If 1 or more of the first 6 patients enrolled within a cohort experience a CTCAE grade 4, non-hematologic, unexpected crenolanib-related adverse event prior to Day 60 then enrollment of additional patients within that cohort will be halted pending review by the Protocol Safety Committee. Otherwise, 6 additional patients will be enrolled within the cohort provided none of the other stopping criteria have been met. Upon enrollment of the 6 additional patients within a cohort, if 2 or more of the patients enrolled within a cohort experience such an event prior to Day 60, then enrollment of additional patients will be halted pending review by the Protocol Safety Committee. If these and the other early stopping criteria are not met, then 12 additional patients will be enrolled to complete the cohort.

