#### **13.3.1. Safety monitoring during the expansion phase**

During the expansion phase, safety monitoring will be performed for the entire per protocol patient population (defined as those who receive at least one dose of study drug) and in a separate analysis dictated by chemotherapy agent used.

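### The two crenolanib-toxicity halting rules count enrolled rather than dosed patients and do not fix the origin of Day 60, so living patients who never take crenolanib can weaken them

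*Combined protocol and SAP*

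**What the plan says.** **Denominator.** The expected-toxicity rule (13.2.2) halts a cohort "If 2 or more of the first 6 patients enrolled within a cohort experience a CTCAE grade 4, non-hematologic, expected crenolanib-related adverse event" before Day 60. After six more patients it halts "if 3 or more of the patients enrolled within a cohort experience such an event prior to Day 60". The unexpected-toxicity rule (13.2.3) halts if "1 or more of the first 6 patients enrolled within a cohort experience a CTCAE grade 4, non-hematologic, unexpected crenolanib-related adverse event" before Day 60, and at the second look if 2 or more do. Section 4 defines enrolled patients as those assigned to a treatment, with no dose required.

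**Other populations in the plan.** Section 13.1.2 says each cohort will "initially enroll 12 patients to receive crenolanib with 1-2 courses of standard induction chemotherapy". For the expansion phase, section 13.3.1 monitors the "per protocol patient population (defined as those who receive at least one dose of study drug" definition. The safety phase has no dosed or evaluable population and no replacement rule.

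**Start of crenolanib.** Section 8.2.1: "Crenolanib will start approximately 24-48 hours after completion of cytarabine (+7 day window". It adds that crenolanib waits until bilirubin, ALT and AST meet the criteria. Section 5.8 puts the start at Day 9. Sections 13.8 and 14.5 do not collect events before the first dose unless a protocol procedure may have caused them.

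**Time origin.** The 13.2.2 limit is breached if the rate of expected "crenolanib-related toxicity with CTCAE severity grade 4 exceeds 20% during the first 60 days of treatment". Section 8.3 says the days of a cycle "are to be counted sequentially from start of chemotherapy (not study drug". Section 13.2 spaces early enrollment by days from the start of induction 1. Section 13.2.1 counts early deaths from the initiation of study treatment, a term the plan does not define. Sections 13.8 and 13.9 use the same term for the drug continued in maintenance.

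**The concern.** These rules are meant to detect a rate of crenolanib toxicity, so the natural denominator is patients who took crenolanib. A patient who withdraws after 7+3, or whose liver tests never permit a start, occupies a place and can contribute only a zero. The required number of events stays the same while fewer patients are at risk. The safety phase decides whether the expansion opens, yet it lacks the dosed-patient definition that the expansion has.

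The undefined Day 60 is a second gap. Two people applying the rule to the same patient could reach different answers about an event on, say, day 65 after chemotherapy began. If the clock starts with chemotherapy, each patient is observed for fewer than 60 crenolanib days.

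**Working it through.** **Inputs from the documents**
- Limits: above 20% (13.2.2) and above 15% (13.2.3).
- Triggers: at least 2 of 6, then 3 of 12 (expected); at least 1 of 6, then 2 of 12 (unexpected). The second count is read as cumulative.
- Crenolanib start: Day 9 (5.8), or about Day 16 with the +7-day window (8.2.1).

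**Assumptions (not in the documents)**
- True rates over 60 crenolanib days: 30% expected; 15% or 25% unexpected.
- Share u of enrolled patients alive but never dosed: 10% or 20%.
- Constant hazard on crenolanib, for the time calculation only.

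**1. The plan's own counts reproduce.** Expected: 1/6 = 16.7% and 2/6 = 33.3%; 2/12 = 16.7% and 3/12 = 25.0%. Unexpected: 1/6 = 16.7%; 1/12 = 8.3% and 2/12 = 16.7%. Each trigger is the smallest count above its limit.

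**2. When a dosed denominator would change a trigger.**
- Expected: 1/5 = 20% does not exceed the limit, but 1/4 = 25% does; 2/10 = 20% does not, but 2/9 = 22.2% does. The written count departs from the 20% limit only if at least 2 of 6 or at least 3 of 12 are undosed. With u = 10%, binomial probabilities are 0.114 and 0.111.
- Unexpected: one event exceeds 15% for any denominator of 6 or fewer, so the first-look count never changes. At 12 it changes only if 6 or more are undosed (probability 0.0005 at u = 10%).

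**3. Chance of halting with living undosed patients.** Per-enrolled rate q = p(1 − u). With X and Y the events in the first and second six, for the expected rule:

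P(halt by 12) = P(X ≥ 2) + P(X = 0)·P(Y ≥ 3) + P(X = 1)·P(Y ≥ 2)

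At q = 0.30: 0.580 + 0.118 × 0.256 + 0.303 × 0.580 = 0.785. The unexpected rule is analogous: P(X ≥ 1) + P(X = 0)·P(Y ≥ 2).

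| Rule, true rate | u = 0 | u = 10% | u = 20% |
|---|---|---|---|
| Expected, 30% | 0.785 | 0.716 | 0.633 |
| Unexpected, 15% | 0.707 | 0.660 | 0.608 |
| Unexpected, 25% | 0.905 | 0.871 | 0.828 |

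At the first look of the expected rule, with a true 30%, the chance of at least 2 events is 58.0% with 6 dosed, 47.2% with 5 and 34.8% with 4.

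**4. Time alone, if Day 60 runs from chemotherapy.** Crenolanib days observed: 60 − 9 = 51, or 60 − 16 = 44. Observed rate = 1 − (1 − p)^(d/60).
- Expected, 30%, d = 51: 1 − 0.70^0.85 = 0.262, and P(halt by 12) = 0.694. With d = 44: 0.230 and 0.604; this requires every patient to start at the outer edge of the window.
- Unexpected, 15%: 0.129 and 0.640 (d = 51), or 0.112 and 0.579 (d = 44).

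**5. If the undosed patients are early deaths instead.** Suppose 10% of enrolled patients die undosed before Day 30, and add the 30-day mortality rule (1 of the first 6, 2 of 12; 13.2.1). Enrollment continues only with no death and at most one toxicity in the first six, then at most one death in the second six and at most two toxicities overall. Per-patient probabilities are 0.10 (death), 0.9 × rate (toxicity) and the remainder. With a 30% expected rate, the chance of halting is 0.89 with no time loss, 0.85 with a Day 9 start and 0.80 with a Day 16 start. All exceed 0.785.

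**The case against.** **Early deaths.** A reader might infer that undosed patients always make the rules less protective. Step 5 shows otherwise: one death before Day 30 among the first six halts the cohort by itself. The second six can absorb one such death, but taken together the rules halt more often, not less. The loss applies to patients who are alive and undosed.

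**Time origin.** A reader might also take it as settled that Day 60 counts from chemotherapy. Section 8.3 and the spacing rule in 13.2 point that way. But 8.3 defines cycle days, which restart at a second induction, and 13.2.1 to 13.2.3 speak of treatment or study treatment without an origin. A crenolanib origin remains possible. Moreover, if treatment means the whole regimen, the 20% and 15% limits are rates over 60 regimen days and are not themselves diluted; only crenolanib exposure is shorter.

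**Who is enrolled.** Inclusion criterion 7 in section 7.1 times the liver tests within 24 hours before crenolanib. The Appendix I checklist times them before induction chemotherapy. The Appendix IV induction key contemplates screening during chemotherapy. Late enrollment would leave fewer undosed patients. These passages conflict and need reconciling; they do not establish that every enrolled patient is dosed.

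**Size and other controls.** The undosed share is not given. Constant hazard is unsupported: with a falling hazard (Weibull shape 0.5, assumed) the Day 9 figure is 0.74 rather than 0.69. The sponsor monitors events continuously (13.2), and data meetings are tied to six-monthly intervals or every six patients (15.2). Section 13.1.2 suggests that treated patients may have been intended all along. These points limit the consequence, but they do not supply the missing definition, and a prespecified trigger should not depend on judgement to repair its denominator.

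**Conclusion.** The denominator point holds on the text. As written, living patients who never receive crenolanib count among the 6 or 12, and nothing in the safety phase excludes or replaces them. On the time window, the supportable finding is an unfixed origin that must be reconciled, not a proven shortening.

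The size is conditional. At an assumed 30% expected rate, the chance of halting by 12 falls from 0.785 to 0.716 or 0.633 with 10% or 20% alive but undosed. It falls to 0.694 from time alone if the origin is chemotherapy, crenolanib starts on Day 9 and the hazard is constant. The 13.2.2 counts contradict their own limit only with at least 2 of 6 or 3 of 12 undosed. In 13.2.3 the thresholds are almost unaffected, and mainly the chance of seeing an event falls. The documents do not support a claim that the effect always runs in the unsafe direction. The halting counts are arithmetically sound.

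**What to change.** - In 13.2.2, 13.2.3 and the matching synopsis text, define the 6 and 12 as the first patients in the cohort who receive at least one dose of crenolanib, in line with 13.3.1. Replace undosed patients for these two rules only.
- State one origin for the 60-day window and reconcile sections 8.3, 13.2, 13.2.1, 13.2.2 and 13.2.3 with it, including how the days run through a second induction. For a rate of crenolanib toxicity, the matching origin is the first crenolanib dose.
- Keep all enrolled patients in the mortality rule, and leave the trigger counts as they are.
- Reconcile the timing of the liver tests between section 7.1 and Appendix I, since it bears on when a patient counts as enrolled.

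The cost is a wording change and the occasional replacement of an undosed patient. If the first dose becomes the origin in place of Day 1 of chemotherapy, each look comes about 8 days (9 − 1) to 15 days (16 − 1) later.

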### **13.2.3. Excessive unexpected crenolanib-related toxicity**

Early stopping rules for excessive unexpected crenolanib-related toxicity will be applied in the safety phase of the study. An unexpected crenolanib-related toxicity is defined as any non-hematologic, adverse event considered related to crenolanib (exclusive of those listed in Section 13.2.2). If the observed rate of unexpected, non-hematologic, crenolanib-related toxicity with CTCAE severity grade 4 exceeds 15% during the first 60 days of treatment then enrollment within a cohort will be halted as follows:

If 1 or more of the first 6 patients enrolled within a cohort experience a CTCAE grade 4, non-hematologic, unexpected crenolanib-related adverse event prior to Day 60 then enrollment of additional patients within that cohort will be halted pending review by the Protocol Safety Committee. Otherwise, 6 additional patients will be enrolled within the cohort provided none of the other stopping criteria have been met. Upon enrollment of the 6 additional patients within a cohort, if 2 or more of the patients enrolled within a cohort experience such an event prior to Day 60, then enrollment of additional patients will be halted pending review by the Protocol Safety Committee. If these and the other early stopping criteria are not met, then 12 additional patients will be enrolled to complete the cohort.

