**Safety analysis:**

During the initial safety phase, twelve patients will be enrolled onto each cohort and if the early stopping rule criterion are not met than approximately 12 additional patients will be enrolled onto each cohort. Safety monitoring will be performed separately for each cohort and enrollment will be halted within a cohort if stopping rules are met for early mortality due to any cause, increase in expected non-hematologic crenolanib-related grade 4 adverse events, or any unexpected non-hematologic crenolanib-related grade 4 adverse events.

Stopping rules during the initial safety phase are the following: If the observed mortality rate exceeds 10 % and 20% at day 30 and 60, respectively, enrollment will be halted pending Protocol Safety Committee review. If an observed increase of expected non-hematologic crenolanib-related grade 4 adverse events exceeds 20% during the first 60 days of treatment further enrollment will be halted pending Protocol Safety Committee review. If an observed increase of unexpected non-hematologic crenolanib-related grade 4 adverse event exceeds 15% during the first 60 days of treatment further enrollment will be halted pending Protocol Safety Committee review.

During the expansion phase, safety monitoring will be performed for the entire per protocol patient population (defined as those who receive at least one dose of study drug) and in a separate analysis dictated by chemotherapy agent used.

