**13.2. Safety monitoring during the initial safety phase**

Adverse events, as defined in Section 14.1, will be monitored during the treatment and post-treatment follow up periods. Adverse events will be monitored on a continuous basis by the sponsor.

The Protocol Safety Committee will review safety data from this trial on a periodic basis. The committee also will monitor the safety outcomes listed below for purposes of determining if enrollment in one or both cohorts should continue or be halted. Within each cohort, up to 6 patients will be initially enrolled. For the first 6 patients, patients will be enrolled in a sequential manner such that no more than 3 patients are within 30 days of starting induction 1 therapy. Enrollment will be halted within a cohort if an apparent increase is observed in the occurrence of one or more of the following outcomes:

- Early mortality due to any cause
- Expected, non-hematologic, crenolanib-related toxicity (CTCAE Grade 4)
- Unexpected, non-hematologic, crenolanib-related toxicity (CTCAE Grade 4)

The criteria used to determine if enrollment will be halted are described in sections 13.2.1, 13.2.2 and 13.3.3.

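### The safety-phase toxicity halts count CTCAE grade 4 only, so an unexpected related event that is fatal on Days 30-59 may trigger nothing, while the same event survived halts the cohort

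*Combined protocol and SAP*

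**What the plan says.** Section 13.2.3 sets the limit for unexpected toxicity as follows: "If the observed rate of unexpected, non-hematologic, crenolanib-related toxicity with CTCAE severity grade 4 exceeds 15% during the first 60 days of treatment", enrollment in that cohort stops. In the first 6 patients this becomes a halt if "1 or more of the first 6 patients enrolled within a cohort experience a CTCAE grade 4, non-hematologic, unexpected crenolanib-related adverse event" before Day 60; after 6 more patients, the count is 2. The synopsis gives the same criterion: "unexpected non-hematologic crenolanib-related grade 4 adverse event exceeds 15% during the first 60 days of treatment". Section 13.2.2 does likewise for expected toxicity, with a limit of 20% and a halt if "2 or more of the first 6 patients enrolled within a cohort experience a CTCAE grade 4, non-hematologic, expected crenolanib-related adverse event", rising to 3 after 12. The list of monitored outcomes in 13.2 also names grade 4 for both classes.

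Deaths enter only through 13.2.1, which counts all causes. The cohort halts "if 1 or more of the first 6 patients enrolled within a cohort die prior to Day 30". For Day 60, "Additionally, enrollment will be halted within a cohort if 2 or more of the patients die prior to Day 60". After the second 6, the counts are 2 (Day 30) and 3 (Day 60).

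Section 14.3 lists death as grade 5, separate from grade 4, and 14.6 has sites enter the highest grade per cycle on the CRF. Nothing says whether a grade 5 related event counts toward a toxicity halt.

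**The concern.** A halting rule should not become less likely to fire as the outcome gets worse. Here it can: a life-threatening related event pauses the cohort for committee review, while a fatal one in the second month may not.

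The mortality rule does not fill the gap. Its Day 60 limit is 20% for deaths from any cause, whereas the limit for unexpected related toxicity is 15%, and the two counts are never added.

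The window is not a remote one. Days run from the start of chemotherapy (8.3) and crenolanib starts at about Day 9 (5.8), or later if delayed. The Day 30 rule therefore covers only about the first three weeks of crenolanib; the rest of the 60-day toxicity window lies outside it.

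**Working it through.** **The plan's own counts.** Each is the smallest x with x/n above the stated rate, and all eight reproduce:

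| Rule | Limit | n = 6 | n = 12 |
|---|---|---|---|
| Death before Day 30 | 10% | 1 (16.7%) | 2 (16.7%) |
| Death before Day 60 | 20% | 2 (33.3%) | 3 (25%) |
| Expected grade 4 | 20% | 2 (33.3%) | 3 (25%) |
| Unexpected grade 4 | 15% | 1 (16.7%) | 2 (16.7%) |

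**One unexpected related event in the first 6, nothing else.**
- Survived at grade 4: 1 event where 1 is needed. The cohort halts.
- Fatal on Days 30-59: 0 grade 4 events (1 needed), 0 deaths before Day 30 (1 needed), 1 death before Day 60 (2 needed). No trigger is met. Counted as toxicity it would be 1/6 = 16.7%.

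**Other patterns that escape**, reading the counts at 12 as cumulative:
- Two such deaths, not both in the first 6: 2/12 = 16.7%.
- Those two deaths plus one unexpected grade 4 event in the second 6: 3/12 = 25%.
- Expected toxicity in the first 6, one grade 4 event plus one such death: 2/6 = 33%. Expected events that are all fatal are caught, because the Day 60 mortality counts are the same (2 and 3); only mixtures escape.

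**Chance of a miss, given one such death and no related event in the other five.** No trigger is met if none of the five dies before Day 60. From 13.2.1, 7.9% die before Day 30 and 19.7% before Day 60. These are relapsed/refractory figures, used here as an assumption.
- Cited mortality: (1 − 0.197)^5 = 33.4%.
- Half of it: (1 − 0.0985)^5 = 59.5%.
- No other deaths: 100%.
- With the newly diagnosed 28-day figure of 10.3% before Day 30 and 11.8% after: (1 − 0.221)^5 = 28.7%.

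**Overall chance of a halt in the first 6, unexpected toxicity.** Patients are taken as independent, in exclusive categories: g = survived grade 4, f = related and fatal on Days 30-59, a = other death before Day 30, b = other death on Days 30-59. Let r = 1 − g − f − a − b.
- As written: P(halt) = 1 − [r^6 + 6(f + b)r^5].
- Grade 4 or 5: P(halt) = 1 − [r^6 + 6b·r^5].
- Gap = 6f·r^5.

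Example: rate 15%, a quarter fatal, cited mortality. Then f = 0.0375, a = 0.079, b = 0.197 − 0.079 = 0.118 and r = 0.653, so r^5 = 0.1187 and r^6 = 0.0775.
- As written: 1 − [0.0775 + 6(0.1555)(0.1187)] = 81.2%.
- Grade 4 or 5: 1 − [0.0775 + 6(0.118)(0.1187)] = 83.8%.

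All cases at a 15% rate. The documents give neither a rate nor a fatal share, so both are assumptions.

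| Other deaths | 25% fatal | 50% fatal | 100% fatal | Grade 4 or 5 |
|---|---|---|---|---|
| Cited mortality | 81.2% | 78.5% | 73.2% | 83.8% |
| Half of it | 68.1% | 62.7% | 51.9% | 73.5% |
| None | 52.3% | 42.3% | 22.4% | 62.3% |

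**By 12 patients, 15% rate, shares 25 / 50 / 100%.**
- Cited mortality: 89.4 v 91.3%, 88.5 v 91.8%, 88.9 v 92.8%.
- No other deaths: 59.2 / 47.9 / 33.1% v 70.7%.

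The by-12 model leaves out related deaths before Day 30. In the second 6, one such death does not trigger the mortality rule either, so these figures are incomplete.

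**Expected toxicity, rate 20%, first 6.** The gap is 30·g·f·r^4. With a quarter fatal, g = 0.15 and f = 0.05.
- Cited mortality: r = 0.603, gap 3.0 points (70.0 v 73.0%).
- No other deaths: r = 0.8, gap 9.2 points (25.2 v 34.5%, each rounded).

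**The case against.** The strongest reply is about the reading. The rule asks whether a patient experiences a grade 4 event; someone treated for a life-threatening event who later dies has done so, and 14.6 governs CRF entry, not the halting count. On that reading, the gap is certain only for deaths with no recognised grade 4 stage. This reading is open, but the protocol does not state it. Likewise, the 15% limit is itself worded for grade 4, so on the literal text 0/6 breaches nothing. The 16.7% shows what the rule would give if it counted the fatal event, not a breach of its wording.

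Second, a related death would hardly pass unseen: "Adverse events will be monitored on a continuous basis by the sponsor". There is also periodic Protocol Safety Committee review (13.2), 24-hour SAE notice and regulatory reporting (14.5), death reporting (14.8), and safety meetings at least every six months or for every 6 patients per cohort (15.2). The IRB or sponsor can stop the study (7.4.3), and what is missed is only a pause for review. All of this limits the consequence, but none of it is an automatic halt.

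Third, the assumed timing is unfavourable to the plan. If half the fatal events fell before Day 30, where the mortality rule catches them in the first 6, a 25% fatal share with cited mortality gives 82.5 v 83.8%. A 10% share gives 83.3 v 83.8%. The gap shrinks but remains.

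**Conclusion.** The point holds as a defect in the automatic trigger, not as an absence of oversight. The contradiction in outcome, where a survived event halts and a fatal one does not, follows from the wording and depends on no assumed rate. It applies in the first 6 patients with no other death before Day 60, and recurs at 12 with two events. Day 30 itself is unclear, because 13.2.1 defines early mortality as within 30 days but counts deaths before Day 30; Days 31-59 are not in doubt.

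The overall loss is modest at the cited mortality: about 3, 5 or 11 points in the first 6 when 25%, 50% or 100% of events are fatal in the window. It grows as other deaths become rarer, to 10, 20 or 40 points with none, which is the upper bound. These figures assume independent patients, a 15% event rate, all fatal events on Days 30-59, and that no fatal event is counted through an earlier grade 4 stage. The point should be fixed; confidence is medium because of that alternative reading.

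**What to change.** Replace 'grade 4' by 'grade 4 or 5' in the halting criteria in the synopsis, 13.2, 13.2.2 and 13.2.3, with all counts and percentages unchanged. If fatal events were always meant to count, this only writes it down.

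The cost is a few words and some additional pauses for committee review, each involving a death judged related to crenolanib. If each patient has an assumed 1% to 2% chance of a fatal unexpected related event on Days 30-59, and there is no other related toxicity, the chance of a pause in the first 6 changes as follows:
- Cited mortality: from 51.0% to 52.9% (at 1%) and from 52.6% to 56.1% (at 2%).
- No other deaths: from 0.15% to 5.9% (at 1%) and from 0.6% to 11.4% (at 2%).
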